6.2.10 Subgroup analysis and exploratory analysis on subgroup cohorts

Based on random grouping, planned subgroup analysis will be performed

on gender, age stratification, ACS presentation, hypertension, diabetes mellitus, history of high low-density lipoprotein cholesterol (LDL-C), history of high lipoprotein(a), prior myocardial infarction, stroke, peripheral vascular disease, COPD, history of CKD-3 or higher, smoking, left main coronary artery disease, SYNTAX Score stratification, EuroScore stratification at baseline, on-pump or off-pump, whether to use the internal thoracic artery, complete revascularization or not.

Multivariable analysis, including GLM and propensity score methods, will be applied to exploratory analysis on subgroup cohorts.

6.2.11 Data Transformation

Date transformation rules are as follows:

1 year = 365.25 days

1 month = 30.4375 days

6.3 Sample Size

A total of 500 subjects were randomized in DACAB study (ticagrelor + aspirin, 168; ticagrelor alone, 166; aspirin alone, 166). There were 5 subjects died before 12-month visit, of these, 2 died in ticagrelor + aspirin group, and 3 died in aspirin alone group.

7. Results of Statistical Analysis

7.1 Primary and secondary objectives

7.1.1 Enrollment and Baseline characteristics

Table 1 Analysis sets

Center	ITT				FAS				PPS			
	A	A+T	T	Total	A	A+T	T	Total	A	A+T	T	Total
1												
2												
3												
4												
5												
Total												

Table 2 Subjects not included in PPS

Random number	Group

Reason: Subjects in the DACAB study who stopped the study drug for more than 60 days.

Table 3 Demographic and baseline characteristics (FAS)

Indicator	A	T+A	T	P
Age				0.***
N(missing)	*** (***)	*** (***)	*** (***)	
mean(sd)	*** (***)	*** (***)	*** (***)	
median	***	***	***	
Min-Max	***~***	***~***	***~***	
p25-p75	***~***	***~***	***~***	
Sex				0.***
N(missing)	*** (***)	*** (***)	*** (***)	
Male	*** (***)	*** (***)	*** (***)	
Female	*** (***)	*** (***)	*** (***)	
Height				
N(missing)	*** (***)	*** (***)	*** (***)	
mean(sd)	*** (***)	*** (***)	*** (***)	
median	***	***	***	
Min-Max	***~***	***~***	***~***	
p25-p75	***~***	***~***	***~***	
Weight				0.***
N(missing)	*** (***)	*** (***)	*** (***)	
mean(sd)	*** (***)	*** (***)	*** (***)	
median	***	***	***	
Min-Max	***~***	***~***	***~***	
p25-p75	***~***	***~***	***~***	
BMI				0.***

Indicator	A	T+A	T	P
N(missing)	*** (***)	*** (***)	*** (***)	
mean(sd)	*** (***)	*** (***)	*** (***)	
median	***	***	***	
Min-Max	***~***	***~***	***~***	
p25-p75	***~***	***~***	***~***	
Clinical status				0.***
N(missing)	*** (***)	*** (***)	*** (***)	
Stable angina	*** (***)	*** (***)	*** (***)	
Unstable angina	*** (***)	*** (***)	*** (***)	
Non - ST-elevation myocardial infarction	*** (***)	*** (***)	*** (***)	
History of myocardial infarction				0.***
N(missing)	*** (***)	*** (***)	*** (***)	
Yes	*** (***)	*** (***)	*** (***)	
No	*** (***)	*** (***)	*** (***)	
Time since onset of myocardial infarction (day)				0.***
N(missing)	*** (***)	*** (***)	*** (***)	
<21	*** (***)	*** (***)	*** (***)	
21-90	*** (***)	*** (***)	*** (***)	
>90	*** (***)	*** (***)	*** (***)	
CCS class				0.***

Indicator	A	T+A	T	P
N(missing)	*** (***)	*** (***)	*** (***)	
0	*** (***)	*** (***)	*** (***)	
I	*** (***)	*** (***)	*** (***)	
II	*** (***)	*** (***)	*** (***)	
III	*** (***)	*** (***)	*** (***)	
IV	*** (***)	*** (***)	*** (***)	
NYHA class				0.***
N(missing)	*** (***)	*** (***)	*** (***)	
I	*** (***)	*** (***)	*** (***)	
II	*** (***)	*** (***)	*** (***)	
III	*** (***)	*** (***)	*** (***)	
IV	*** (***)	*** (***)	*** (***)	
History of hypertension				0.***
N(missing)	*** (***)	*** (***)	*** (***)	
Yes	*** (***)	*** (***)	*** (***)	
No	*** (***)	*** (***)	*** (***)	
History of hyperlipidemia				0.***
N(missing)	*** (***)	*** (***)	*** (***)	
Yes	*** (***)	*** (***)	*** (***)	
No	*** (***)	*** (***)	*** (***)	
History of smoking				0.***
N(missing)	*** (***)	*** (***)	*** (***)	
Yes	*** (***)	*** (***)	*** (***)	

Indicator	A	T+A	T	P
No	*** (***)	*** (***)	*** (***)	
History of diabetes				0.***
N(missing)	*** (***)	*** (***)	*** (***)	
Yes	*** (***)	*** (***)	*** (***)	
No	*** (***)	*** (***)	*** (***)	
History of peripheral vascular disease				0.***
N(missing)	*** (***)	*** (***)	*** (***)	
Yes	*** (***)	*** (***)	*** (***)	
No	*** (***)	*** (***)	*** (***)	
History of cerebrovascular accident				0.***
N(missing)	*** (***)	*** (***)	*** (***)	
Yes	*** (***)	*** (***)	*** (***)	
No	*** (***)	*** (***)	*** (***)	
History of peptic ulcer disease				0.***
N(missing)	*** (***)	*** (***)	*** (***)	
Yes	*** (***)	*** (***)	*** (***)	
No	*** (***)	*** (***)	*** (***)	
History of chronic kidney disease				0.***
N(missing)	*** (***)	*** (***)	*** (***)	

Indicator	A	T+A	T	P
Yes	*** (***)	*** (***)	*** (***)	
No	*** (***)	*** (***)	*** (***)	
				0.***
LVEDD(mm)				0.***
N(missing)	*** (***)	*** (***)	*** (***)	
mean(sd)	*** (***)	*** (***)	*** (***)	
median	***	***	***	
Min-Max	***~***	***~***	***~***	
p25-p75	***~***	***~***	***~***	
LVEF(%)				0.***
N(missing)	*** (***)	*** (***)	*** (***)	
mean(sd)	*** (***)	*** (***)	*** (***)	
median	***	***	***	
Min-Max	***~***	***~***	***~***	
p25-p75	***~***	***~***	***~***	
LVEF class				0.***
N(missing)	*** (***)	*** (***)	*** (***)	
30%-50%	*** (***)	*** (***)	*** (***)	
>50%	*** (***)	*** (***)	*** (***)	
SYNTAX score				0.***
N(missing)	*** (***)	*** (***)	*** (***)	
Low(0-22)	*** (***)	*** (***)	*** (***)	
Intermediate(23-32)	*** (***)	*** (***)	*** (***)	
High(>=33)	*** (***)	*** (***)	*** (***)	
EuroScore score				0.***

Indicator	A	T+A	T	P
N(missing)	*** (***)	*** (***)	*** (***)	
Low(0-2)	*** (***)	*** (***)	*** (***)	
Medium(3-5)	*** (***)	*** (***)	*** (***)	
High(>=6)	*** (***)	*** (***)	*** (***)	
Aspirin				0.***
N(missing)	*** (***)	*** (***)	*** (***)	
Yes	*** (***)	*** (***)	*** (***)	
No	*** (***)	*** (***)	*** (***)	
beta_Blocker				0.***
N(missing)	*** (***)	*** (***)	*** (***)	
Yes	*** (***)	*** (***)	*** (***)	
No	*** (***)	*** (***)	*** (***)	
ACEI or ARB				0.***
N(missing)	*** (***)	*** (***)	*** (***)	
Yes	*** (***)	*** (***)	*** (***)	
No	*** (***)	*** (***)	*** (***)	
Statins				0.***
N(missing)	*** (***)	*** (***)	*** (***)	
Yes	*** (***)	*** (***)	*** (***)	
No	*** (***)	*** (***)	*** (***)	
Proton pump inhibitor				0.***
N(missing)	*** (***)	*** (***)	*** (***)	
Yes	*** (***)	*** (***)	*** (***)	

Indicator	A	T+A	T	P
No	*** (***)	*** (***)	*** (***)	
Cardiopulmonary bypass usage				0.***
N(missing)	*** (***)	*** (***)	*** (***)	
Yes	*** (***)	*** (***)	*** (***)	
No	*** (***)	*** (***)	*** (***)	
Total grafts	***	***	***	
Graft type				
- LIMA	*** (***)	*** (***)	*** (***)	
- RA	*** (***)	*** (***)	*** (***)	
- SVG	*** (***)	*** (***)	*** (***)	
Mean total grafts/case	***	***	***	
Mean SVG/case	***	***	***	

Table 4 Baseline laboratory examinations (FAS)

Indicator	A	T+A	T	P
Glycosylated hemoglobin				0.***
N(missing)	*** (***)	*** (***)	*** (***)	
mean(sd)	*** (***)	*** (***)	*** (***)	
median	***	***	***	
Min-Max	***~***	***~***	***~***	
p25-p75	***~***	***~***	***~***	
Low density lipoprotein				
N(missing)	*** (***)	*** (***)	*** (***)	
mean(sd)	*** (***)	*** (***)	*** (***)	
median	***	***	***	
Min-Max	***~***	***~***	***~***	
p25-p75	***~***	***~***	***~***	
Ditto for other laboratory examination indicators				

7.1.2 Primary Outcome

Table 5 Occurrence of MACE4 during follow-up (FAS)

Group	Overall occurrence of the event	Event rate during follow-up				
		12 months	24 months	36 months	48 months	60 months
A	*** (***)	**%	**%	**%	**%	**%
T+A	*** (***)	**%	**%	**%	**%	**%
T	*** (***)	**%	**%	**%	**%	**%

Note: Overall occurrence of the event includes all the events during the follow-up period, KM was used to estimate the event rates in different visit.

Table 6 Survival Analysis for MACE4 event during follow-up (FAS)

Group	HR(95% CI)	Logrank P
T+A VS. A	*** (***, ***)	0. ****
T VS. A	*** (***, ***)	0. ****
T+A VS. T	*** (***, ***)	0. ****

Figure 1. Kaplan-Meier curves of MACE4 during the follow-up (FAS)

Table 7 Occurrence of MACE4 during follow-up (PP)

Group	Overall occurrence of the event	Event rate during follow-up				
		12 months	24 months	36 months	48 months	60 months
A	*** (***)	**%	**%	**%	**%	**%
T+A	*** (***)	**%	**%	**%	**%	**%
T	*** (***)	**%	**%	**%	**%	**%

Note: Overall occurrence of the event includes all the events during the follow-up period, KM was used to estimate the event rates in different visit.

Table 8 Survival Analysis for MACE4 event during follow-up (PP)

Group	HR(95% CI)	Logrank P
T+A VS. A	*** (***,***)	0. ****
T VS. A	*** (***,***)	0. ****
T+A VS. T	*** (***,***)	0. ****

Figure 2. Kaplan-Meier curves of MACE4 during the follow-up (PP)

7.1.3 Secondary Outcomes

Table 9 Occurrence of secondary outcomes during the follow-up (FAS)

Indicator/Group	Overall occurrence of the event	Event rate during follow-up				
		12 months	24 months	36 months	48 months	60 months
MACE5						
A	*** (***)	**%	**%	**%	**%	**%
T+A	*** (***)	**%	**%	**%	**%	**%
T	*** (***)	**%	**%	**%	**%	**%
MACE3						
A	*** (***)	**%	**%	**%	**%	**%
T+A	*** (***)	**%	**%	**%	**%	**%
T	*** (***)	**%	**%	**%	**%	**%
All-cause death						
A	*** (***)	**%	**%	**%	**%	**%
T+A	*** (***)	**%	**%	**%	**%	**%
T	*** (***)	**%	**%	**%	**%	**%
Cardiovascular death						
A	*** (***)	**%	**%	**%	**%	**%
T+A	*** (***)	**%	**%	**%	**%	**%
T	*** (***)	**%	**%	**%	**%	**%

Event rate during follow-up

Indicator/Group	Overall occurrence of the event	12 months	24 months	36 months	48 months	60 months
Myocardial infarction						
A	*** (***)	**%	**%	**%	**%	**%
T+A	*** (***)	**%	**%	**%	**%	**%
T	*** (***)	**%	**%	**%	**%	**%
Stroke						
A	*** (***)	**%	**%	**%	**%	**%
T+A	*** (***)	**%	**%	**%	**%	**%
T	*** (***)	**%	**%	**%	**%	**%
Coronary revascularization						
A	*** (***)	**%	**%	**%	**%	**%
T+A	*** (***)	**%	**%	**%	**%	**%
T	*** (***)	**%	**%	**%	**%	**%
Hospitalization for unstable angina						
A	*** (***)	**%	**%	**%	**%	**%
T+A	*** (***)	**%	**%	**%	**%	**%
T	*** (***)	**%	**%	**%	**%	**%

Note: Overall occurrence of the event includes all the events during the follow-up period, KM was used to estimate the event rates in different visit.

Table 10 Survival analysis for secondary outcomes during follow-up (FAS)

Indicator/Group	HR(95% CI)	Logrank P
MACE5		
T+A VS. A	*** (***, ***)	0. ****
T VS. A	*** (***, ***)	0. ****
T+A VS. T	*** (***, ***)	0. ****
MACE3		
T+A VS. A	*** (***, ***)	0. ****
T VS. A	*** (***, ***)	0. ****
T+A VS. T	*** (***, ***)	0. ****
All-cause death		
T+A VS. A	*** (***, ***)	0. ****
T VS. A	*** (***, ***)	0. ****
T+A VS. T	*** (***, ***)	0. ****
Cardiovascular death		
T+A VS. A	*** (***, ***)	0. ****
T VS. A	*** (***, ***)	0. ****
T+A VS. T	*** (***, ***)	0. ****
Myocardial infarction		
T+A VS. A	*** (***, ***)	0. ****
T VS. A	*** (***, ***)	0. ****
T+A VS. T	*** (***, ***)	0. ****
Stroke		

Indicator/Group	HR(95% CI)	Logrank P
T+A VS. A	*** (***,***)	0. ****
T VS. A	*** (***,***)	0. ****
T+A VS. T	*** (***,***)	0. ****
 Coronary revascularization		
T+A VS. A	*** (***,***)	0. ****
T VS. A	*** (***,***)	0. ****
T+A VS. T	*** (***,***)	0. ****
 Hospitalization for unstable angina		
T+A VS. A	*** (***,***)	0. ****
T VS. A	*** (***,***)	0. ****
T+A VS. T	*** (***,***)	0. ****

Figure 3. Kaplan-Meier curves of MACE5 during follow-up (FAS)

Figure 4. Kaplan-Meier curves of MACE3 during follow-up (FAS)

Figure 5. Kaplan-Meier curves of all-cause death during follow-up (FAS)

Figure 6. Kaplan-Meier curves of cardiovascular death during follow-up (FAS)

Figure 7. Kaplan-Meier curves of myocardial infarction during follow-up (FAS)

Figure 8. Kaplan-Meier curves of stroke during follow-up (FAS)

Figure 9. Kaplan-Meier curves of coronary revascularization during follow-up (FAS)

Figure 10. Kaplan-Meier curves of hospitalization for unstable angina during follow-up (FAS)

Table 11 Grafts during follow-up (FAS)

Indicator	A	T+A	T	P
CTA/CAG visit time (month)				0.***
N(missing)	*** (***)	*** (***)	*** (***)	
mean(sd)	*** (***)	*** (***)	*** (***)	
median	***	***	***	
Min-Max	***~***	***~***	***~***	
p25-p75	***~***	***~***	***~***	
Reexamination situation of grafts				0.***
N(missing)	*** (***)	*** (***)	*** (***)	
Examined	*** (***)	*** (***)	*** (***)	
Not examined	*** (***)	*** (***)	*** (***)	

Table 12 Patency of different grafts (FAS)

	LIMA	SVG	RA	Total
7 days after surgery				
Patency (A)	***	***	***	***
Failure (O/B)	**	**	**	**
Patency rate	***%	***%	***%	***%
7 days-1 month after surgery				
Patency (A)	***	***	***	***
Failure (O/B)	**	**	**	**
Patency rate	***%	***%	***%	***%
1 month-1 year after surgery				
Patency (A)	***	***	***	***
Failure (O/B)	**	**	**	**
Patency rate	***%	***%	***%	***%
1 year-5 years after surgery				
Patency (A)	***	***	***	***
Failure (O/B)	**	**	**	**
Patency rate	***%	***%	***%	***%

Table 13 Comparison of graft patency rates in different treatment group (using grafts as subjects)

	Patency rate(95%CI)			A+T VS. A			T VS. A			A+T VS. T		
	A+T		T	Rate difference (95%CI)	RR(95%CI)	p	Rate difference (95%CI)	RR(95%CI)	p	Rate difference (95%CI)	RR(95%CI)	p
	A	A										
Total grafts	***	***	***									
Patency rate 7 days after surgery	***%	***%	***%	***%	0.**	0.***	***%	0.**	0.***	***%	0.**	0.***
	(***% to ***%)	(***% to ***%)	(***% to ***%)	(***% to ***%)	(0.** to 0.**)		(***% to ***%)	(0.** to 0.**)		(***% to ***%)	(0.** to 0.**)	
Patency rate 7 days-1 month after surgery	***%	***%	***%	***%	0.**	0.***	***%	0.**	0.***	***%	0.**	0.***
	(***% to ***%)	(***% to ***%)	(***% to ***%)	(***% to ***%)	(0.** to 0.**)		(***% to ***%)	(0.** to 0.**)		(***% to ***%)	(0.** to 0.**)	
Patency rate 1 month-1 year after surgery	***%	***%	***%	***%	0.**	0.***	***%	0.**	0.***	***%	0.**	0.***
	(***% to ***%)	(***% to ***%)	(***% to ***%)	(***% to ***%)	(0.** to 0.**)		(***% to ***%)	(0.** to 0.**)		(***% to ***%)	(0.** to 0.**)	
Patency rate 1-5 years after surgery	***%	***%	***%	***%	0.**	0.***	***%	0.**	0.***	***%	0.**	0.***
	(***% to ***%)	(***% to ***%)	(***% to ***%)	(***% to ***%)	(0.** to 0.**)		(***% to ***%)	(0.** to 0.**)		(***% to ***%)	(0.** to 0.**)	
Saphenous vein graft	S	***	***	***								

Patency rate(95%CI)			A+T VS. A			T VS. A			A+T VS. T		
A+T		T	Rate difference (95%CI)	RR(95%CI)	p	Rate difference (95%CI)	RR(95%CI)	p	Rate difference (95%CI)	RR(95%CI)	p
A											
Patency rate 1-5 years after surgery	***%	***%	***%	***%	0.**	***%	0.**	0.***	***%	0.**	0.***
	(***% to ***%)	(***% to ***%)	(***% to ***%)	(***% to ***%)	(0.** to 0.**) 0.***	(***% to ***%)	(0.** to 0.**) 0.***	(***% to ***%)	(***% to ***%)	(0.** to 0.**) 0.***	

Note: rate difference, RR and p value were estimated by GEE.

7.1.4 Laboratory examination during follow-up

Table 14 Laboratory examinations during follow-up (FAS)

Indicator	A	T+A	T	P
Glycosylated hemoglobin				0.***
N(missing)	*** (***)	*** (***)	*** (***)	
mean(sd)	*** (***)	*** (***)	*** (***)	
median	***	***	***	
Min-Max	***~***	***~***	***~***	
p25-p75	***~***	***~***	***~***	
Low density lipoprotein				
N(missing)	*** (***)	*** (***)	*** (***)	
mean(sd)	*** (***)	*** (***)	*** (***)	
median	***	***	***	
Min-Max	***~***	***~***	***~***	
p25-p75	***~***	***~***	***~***	

Ditto for other laboratory examination indicators

7.1.5 Concomitant medications and bleeding events

Table 15 Concomitant medications during follow-up

Indicator	A	T+A	T	P
Drug1				0.***
N(missing)	*** (***)	*** (***)	*** (***)	
Use	*** (***)	*** (***)	*** (***)	
Not use	*** (***)	*** (***)	*** (***)	
Drug2				0.***
N(missing)	*** (***)	*** (***)	*** (***)	
Use	*** (***)	*** (***)	*** (***)	
Not use	*** (***)	*** (***)	*** (***)	
Ditto for other drugs				

Table 16 Bleeding events during follow-up

Indicator	A	T+A	T	P
Cerebral hemorrhage				0.***
N(missing)	*** (***)	*** (***)	*** (***)	
Occur	*** (***)	*** (***)	*** (***)	
Not occur	*** (***)	*** (***)	*** (***)	
Massive gastrointestinal hemorrhage				0.***
N(missing)	*** (***)	*** (***)	*** (***)	
Occur	*** (***)	*** (***)	*** (***)	
Not occur	*** (***)	*** (***)	*** (***)	

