### **9.3 Determination of Sample Size**

A total of 500 subjects were randomized in DACAB study (ticagrelor + aspirin, 168; ticagrelor alone, 166; aspirin alone, 166). There are 5 subjects died before 12-month visit, of these, 2 died in ticagrelor + aspirin group, and 3 died in aspirin alone group. Therefore, 495 patients would be scheduled for 5-year on-site visit.

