There are 500 patients were enrolled from July 2014 through November 2015 and follow-up was completed in January 2017, 168 patients in the T+A group, 166 in T group and 166 in A group. The results showed that the 1-year SVG patency rate (primary endpoint) of T+A group was 88.7% (432/487, T+A vs A, p=0.0006), the T group was 82.8% (371/485, T vs A, p=0.0962), and the A group was 76.5% (404/488). The incidence of MACE during 1 year of follow-up was 1.8% in T+A group, 2.4% in T group, and 5.4% in A group. The DACAB trial demonstrated that compared with aspirin monotherapy, the combination of ticagrelor and aspirin significantly improved 1-year SVG patency after CABG. Meanwhile, the combination of ticagrelor and aspirin therapy or ticagrelor monotherapy showed a favor trend with reducing the MACEs compared with aspirin monotherapy.

Would the observed differences in SVG patency at 1 year post CAGB translate into long-term clinical benefit? This remain to be a great interest to follow up these patients. Therefore, in present study, we intend to collect and analyze the long-term data in patients who were enrolled and survived in DACAB trial. We would observe the clinical outcomes of these subjects at 5-year post-CABG.

2. Study Objectives

- Primary Objective**

The primary objective is to compare the incidence of major adverse clinical events-4 (MACE-4, a composite of all-cause death, myocardial infarction, stroke, and coronary revascularization) among 3 randomized regimens in previous DACAB trial in the extended five-year follow-up after CABG.

- Secondary Objectives**

The secondary objectives are to compare the incidence of MACE-5 (a composite of all-cause death, myocardial infarction, stroke, coronary revascularization and hospitalization for unstable angina); MACE-3 (a composite of cardiovascular death, myocardial infarction and stroke); all-cause death; cardiovascular death; myocardial infarction; stroke; coronary revascularization; hospitalization for unstable angina and graft failure among 3 randomized regimens in previous DACAB trial in the five-year follow-up after CABG.

- Exploratory Objectives**

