6.2 Methods of Statistical Analyses

6.2.1 General Method of Analysis

Counts and percentages for discrete variables, and mean, SD, maximum, minimum, median, 25th percentiles and 75th percentiles for continuous

variables will be used to summarize data.

The missing data will be assumed missing at random, no imputation will be applied unless specified otherwise.

A 2-sided level of significance of .05 will be applied to all statistical analyses unless specified otherwise. Statistical analyses will be performed using SAS 9.4.

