6.2.6 Bleeding Events

Descriptive statistical analysis will be applied to bleeding events including cerebral hemorrhage and massive gastrointestinal hemorrhage associated with antiplatelet therapy.

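### Table 16 prints one three-arm P value per bleed type with no named test and no planned pairwise effect or confidence interval, although SAP 6.2.6 calls the bleeding analysis descriptive

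*SAP*

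**What the plan says.** On method, SAP 6.2.6 says: "Descriptive statistical analysis will be applied to bleeding events including cerebral hemorrhage and massive gastrointestinal hemorrhage associated with antiplatelet therapy". It names no test, effect measure or interval, and no rule for reading the result.

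The matching shell in SAP 7.1.5, "Table 16 Bleeding events during follow-up", has columns for A, T+A, T and P. It covers two bleed types, cerebral hemorrhage and massive gastrointestinal hemorrhage. Each has rows for the number with data, the number with the event and the number without, and one P.

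SAP 6.2.1 sets the general rule: "A 2-sided level of significance of .05 will be applied to all statistical analyses unless specified otherwise". Chi-square and Fisher's exact tests for yes/no data are named only in SAP 6.2.9, for the cohorts defined by graft failure at one year.

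Other tables are built differently. Tables 6 and 10 give hazard ratios with 95% confidence intervals for T+A vs A, T vs A and T+A vs T. Table 13 gives pairwise differences and ratios of patency rates with intervals. Table 17 gives pairwise hazard ratios with intervals within subgroups.

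**The concern.** The text and the shell do not agree. A descriptive analysis needs no P; a comparative one needs a named test and an estimate of the size of the difference. As drafted, the table supplies a P across three arms and leaves out the contrast a reader would set beside the efficacy hazard ratios, T+A vs A.

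This matters because SAP 6.2.6 itself ties these bleeds to antiplatelet therapy, and the randomized comparison is between dual and single antiplatelet regimens. If bleeds are few, the P will often exceed .05 when a material excess is present. Printed without an interval, next to MACE results that have one, such a P is easily read as reassurance. A P below .05 would not say which arm is responsible.

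**Working it through.** **Inputs from the documents.** Arm sizes are A 166, T+A 168 and T 166 (SAP 6.3), and 166 + 168 + 166 = 500. The default level is two-sided .05 (SAP 6.2.1). The documents state no power, event count or precision for bleeding, so there is no planned figure to reproduce.

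**Assumptions.** No bleeding rate is given. I take 1% to 5% over five years in A for a given bleed type, with T+A at two or three times that rate and T equal either to A or to T+A. As no test is named, I use both natural candidates: the three-group Fisher-Freeman-Halton exact test and the 2-df Pearson chi-square. Everyone is counted as fully followed; losses would lower the power.

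**Step 1: power of the three-group test.** Power is the sum, over all triples of counts, of Bin(a; 166, pA) × Bin(b; 168, pT+A) × Bin(c; 166, pT), taken where P ≤ .05. Ranges run over the two tests and the two settings for T.

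| Rate in A | Power, T+A doubled | Power, T+A tripled |
|---|---|---|
| 1% | 7–10% | 19–28% |
| 2% | 15–20% | 43–53% |
| 3% | 23–27% | 64–71% |
| 5% | 39–44% | 90–92% |

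A doubling is missed more often than not in every row. A tripling is missed about half the time at 2% and more often at 1%, but is usually found at 3% and nearly always at 5%.

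**Step 2: pairwise scale.** For 80% power in one pairwise comparison, n per arm = [1.96√(2p̄(1−p̄)) + 0.84√(p₁(1−p₁)+p₂(1−p₂))]² / (p₁−p₂)². For a doubling this gives 2319, 1141, 749 and 435 per arm at A rates of 1%, 2%, 3% and 5%, against about 166 available. The 80% is a conventional yardstick; the documents set no power target.

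**Step 3: what the table would hide.** Take 3, 9 and 3 bleeds in A, T+A and T.
- Three-group exact P = 0.12; chi-square P = 0.09.
- Rates: 9/168 = 5.36% and 3/166 = 1.81%; difference 3.55 points.
- Wilson 95% limits: T+A 2.84% to 9.87%; A 0.62% to 5.18%.
- Newcombe lower limit: 3.55 − √((5.36−2.84)² + (5.18−1.81)²) = 3.55 − 4.20 = −0.65.
- Newcombe upper limit: 3.55 + √((9.87−5.36)² + (1.81−0.62)²) = 3.55 + 4.66 = +8.21.

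The P alone would be non-significant, while the interval is compatible with an excess of about 8 points.

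**Step 4: equal observed counts.** With 3 bleeds in each of T+A and A, the three-group P is 1.0 (T also 3), yet the Newcombe interval is −3.6 to +3.5 points. On the ratio scale, with upper limit RR × exp(1.96√(1/b − 1/168 + 1/a − 1/166)), equal counts of 5, 8 and 15 per arm give upper limits of 3.35, 2.57 and 1.96. Five bleeds per arm (3%) do not exclude a tripling and eight (about 5%) do. Excluding a doubling takes about fifteen per arm (about 9%).

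**The case against.** The best defence is that bleeding is neither a primary nor a secondary outcome. Protocol 5.4 makes the efficacy outcomes the main safety outcomes, and Protocol 5.4.2 lists gastrointestinal bleeding among other serious events. Lighter treatment is consistent with that ranking. The A / T+A / T / P layout is also a general shell, used in Tables 3, 4, 11, 14 and 15, and was not devised for bleeding. This explains the layout, but it does not reconcile the P with 6.2.6 or supply the missing interval. Table 17 gives pairwise intervals to exploratory subgroups, so ranking alone does not account for the gap.

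Four stronger readings are tempting, and the documents do not support them.
- *The plan judges bleeding by P above or below .05.* No decision rule, margin or conclusion of no difference is written. The .05 in 6.2.1 sets the level for tests and does not turn a descriptive table into a verdict.
- *The table gives no estimate.* Counts and percentages per arm are printed, so a reader can derive crude contrasts and intervals, as Step 3 does. What is missing is a planned pairwise effect with its interval.
- *A tripling would usually be missed.* That depends on rates the documents do not give, and it fails at A rates of 3% and above.
- *No other comparison touches bleeding.* Protocol 5.3.2 includes hemorrhagic stroke within stroke, and Table 10 gives pairwise hazard ratios for stroke. The cover is partial: ischemic and hemorrhagic strokes are pooled, and gastrointestinal bleeding is not addressed.

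It is also true that the change adds no precision.

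**Conclusion.** The point stands as one of reporting and consistency. SAP 6.2.6 and Table 16 disagree on whether bleeding is compared. The one comparison specific to bleeding is a three-arm P from an unnamed test, with no pairwise effect or interval.

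On the assumed A rates of 1% to 5%, full follow-up and either candidate test, a true doubling in T+A yields P>.05 in roughly 56% to 93% of trials. A tripling yields it about half the time or more only at A rates up to about 2%. The conclusion about doubling would weaken if bleeding were much commoner than 5% in A.

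The primary analysis is not affected. The correction is cheap and should be made, because it determines how bleeding is read alongside the MACE hazard ratios.

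**What to change.** In Table 16, keep the counts and percentages and replace the single P column with T+A vs A, T vs A and T+A vs T contrasts for each bleed type. Give either the risk difference with a Newcombe 95% confidence interval or, to match Tables 6 and 10 and allow for censoring, the hazard ratio with a 95% confidence interval, using an exact or Firth method if events are sparse. If a P is kept, name its test.

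Reword SAP 6.2.6 to match the table. State there that P>.05, or an interval that includes no effect, will not be reported as absence of a bleeding difference.

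The cost is a short text change and a few extra columns in one table, with no new data. The intervals will be wide and will show openly that this cohort may be unable to rule out a material excess of bleeding.

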## 1.2 Study Purpose

This study is designed to compare the clinical outcomes of the subjects enrolled in the DACAB trial 5 years after CABG (randomization).

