# **3. STUDY PLAN AND PROCEDURES**

## **3.1 Overall Study Design and Flow Chart**

This study will include the subjects who enrolled in DACAB trial to compare clinical outcomes 5 years after CABG. After completing 12-month randomized treatment from DACAB trial, investigators would not make any interventions or impact on subjects' therapeutic strategy.

Aspirin monotherapy would be given to most subjects according to the current guidelines. However, other antiplatelet regimens might be given for subjects by their attending physician based on the subject's individual condition. Subjects would spontaneously undergo regular laboratory test such as biochemical parameters, ECG, UCG, coronary computed tomography angiography imaging (CCTA) or coronary angiography (CAG) and clinical follow-up according to clinical need and their individual condition. At 5-year ( $\pm$  3 month) after CABG, a face-to-face visit is scheduled to be performed to collect the occurrence of clinical events, including types and time of events. The first 5-year visit would be performed around August 2019.

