4.3 Evaluation and Calculation of Endpoints

The primary outcome is the time to the first occurrence of any MACE-4, which is a composite of all-cause death, myocardial infarction, stroke, and coronary revascularization and measured in days since the date of randomization. Subjects who had not experienced any major adverse clinical events from randomization to the last visit will be right-censored. For those subjects who lost to follow-up at 5-year visit, the date of the last contact and the most updated clinical outcomes available in medical record or other source will be used in primary analysis. If there's no major adverse clinical events recorded for those subjects who lost to follow-up at 5-year visit, then these subjects will be right-censored at the date of their last contact. The survival curves will be estimated using Kaplan-Meier method.

The secondary outcomes (time to event) will be analyzed similarly with the primary observational endpoint.

Graft failure after CABG is in accordance with Fitzgibbon classification criteria by using MSCTA or CAG, there were a total of 3 categories, grade A, B and O, where grade A accounted for graft patency (no lesions), and grade B/O accounted for the graft failure.

5. Subject Selection Criteria

All the subjects enrolled in the DACAB trial.

6. Statistical Analysis

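### SAP Table 16 pools bleeding into one raw proportion over an undefined follow-up, with no split at month 12 and no censoring, although the randomised regimens differed only in months 0-12

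*SAP*

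**What the plan says.** SAP 6.2.6 is one sentence: "Descriptive statistical analysis will be applied to bleeding events including cerebral hemorrhage and massive gastrointestinal hemorrhage associated with antiplatelet therapy". The matching shell in SAP 7.1.5, "Table 16 Bleeding events during follow-up", has columns for A, T+A, T and P. For each of the two bleeding types it has rows for N(missing), Occur and Not occur. It gives no start or end date, time points, person-time or censoring rule.

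On treatment, Protocol 3.1 says: "After completing 12-month randomized treatment from DACAB trial, investigators would not make any interventions". For the later years it says: "Aspirin monotherapy would be given to most subjects according to the current guidelines". It also allows other antiplatelet regimens at the treating physician's choice. Follow-up runs to about five years after CABG (Protocol 1.2 and 3.1).

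The clinical outcomes are handled differently. Under SAP 4.3, subjects lost before the 5-year visit with no recorded event are kept up to the time they were last known: "these subjects will be right-censored at the date of their last contact". Tables 5, 7 and 9 have columns at 12, 24, 36, 48 and 60 months, with the note "Overall occurrence of the event includes all the events during the follow-up period, KM was used to estimate the event rates in different visit". Tables 12 and 13 separate graft patency before and after one year.

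**The concern.** SAP 6.2.6 concerns bleeding linked to antiplatelet therapy, and the arms differed in assigned antiplatelet therapy only in the first year. A single five-year proportion mixes that year with about four years in which no difference was assigned, so the reader cannot see bleeding while the regimens were being taken. For MACE-4 the reader does see a 12-month rate by arm.

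The background sections of both documents give first-year patency and MACE but no first-year bleeding. Table 16 is therefore the only planned comparison of bleeding as such across the arms. At stake is whether the harm side of T+A against aspirin can be read for the same periods as the benefit side.

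There is a second, separate gap. The SAP does not say whether a subject lost before the 5-year visit goes under N(missing), which discards the time observed, or under Not occur, which treats unobserved time as free of bleeding.

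**Working it through.** **No figure to reproduce.** The documents give no bleeding rate, bleeding effect size or power. What follows is an illustration.

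**Inputs from the documents**
- Randomised treatment: 12 months (Protocol 3.1).
- Follow-up: about 60 months (Protocol 1.2).
- Arm sizes: "ticagrelor + aspirin, 168; ticagrelor alone, 166; aspirin alone, 166" (SAP 6.3).
- Two-sided 0.05 (SAP 6.2.1).

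**Assumptions, not in the documents**
- Aspirin-arm bleeding risk p of 0.5% to 2% per year, constant over time.
- First-year hazard ratio R of 1.5 to 3.
- Equal hazards in all arms after month 12.

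**Step 1. Share of time with an assigned difference.** 12/60 = 20%.

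**Step 2. Rate ratio over months 0-60.** One year at ratio R and four years at ratio 1 give (R + 4)/5:
- R = 1.5: 5.5/5 = 1.10
- R = 2: 6/5 = 1.20
- R = 3: 7/5 = 1.40

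If the aspirin-arm first-year rate is k times its later yearly rate, the ratio is (kR + 4)/(k + 4):

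| k | R = 2 | R = 3 |
|---|---|---|
| 0.5 | 5/4.5 = 1.11 | 5.5/4.5 = 1.22 |
| 1 | 1.20 | 1.40 |
| 2 | 8/6 = 1.33 | 10/6 = 1.67 |

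With stronger clustering in year 1 the attenuation shrinks: k = 4 and R = 2 gives 12/8 = 1.50.

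**Step 3. Proportions, as Table 16 would show them.** With h = -ln(1 - p), the control risk is 1 - exp(-h) at 12 months and 1 - exp(-5h) at 60. The treated risk is 1 - exp(-Rh) and 1 - exp(-(R + 4)h). Power is for two arms of 166 and 168, by normal approximation.

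| p per year, R | 12 months, A v T+A | Difference (points) | Power | 60 months, A v T+A | Difference (points) | Power |
|---|---|---|---|---|---|---|
| 1%, 2 | 1.00% v 1.99% | 0.99 | 11% | 4.90% v 5.85% | 0.95 | 6% |
| 1%, 3 | 1.00% v 2.97% | 1.97 | 25% | 4.90% v 6.79% | 1.89 | 11% |
| 2%, 3 | 2.00% v 5.88% | 3.88 | 44% | 9.61% v 13.19% | 3.58 | 18% |

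The risk ratio falls from 1.99 to 1.19 in the first row, from 2.97 to 1.39 in the second and from 2.94 to 1.37 in the third. The approximation is rough with so few events, and Table 16 shows one P per bleeding type across three arms, so the power figures show direction only.

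**Step 4. Absolute difference.** The 60-month difference equals the 12-month difference times exp(-4h) = (1 - p)^4. That factor is 0.98, 0.96 and 0.92 for p = 0.5%, 1% and 2%. The excess stays almost whole, while the later events added to both arms make it harder to see as a ratio or in a test.

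**Step 5. Loss after month 12, counted as Not occur** (loss rates assumed; p = 1%, R = 2).
- Equal loss of 0%, 10% and 20% gives risk ratios of 1.19, 1.21 and 1.23. The raw control proportion falls from 4.90% to 4.12% at 20% loss.
- Unequal loss moves the ratio either way: 5% in T+A and 15% in A gives 1.31; 15% and 5% gives 1.12.

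**Step 6. The other reading of the period.** If follow-up in Table 16 means only the extension, months 12-60, none of the on-treatment bleeding is in the table. The MACE tables count from randomisation, so 0-60 months is the likelier reading, but the SAP does not say so for bleeding.

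**The case against.** The strongest reply has four parts.

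1. **The study compares randomised regimens over five years.** A whole-period bleeding comparison by arm matches that purpose and is not in itself a wrong denominator. The MACE-4 hazard ratios and log-rank tests in Table 6 also cover the whole period, and the 12-month column of Table 5 has no test or interval. This stands: a reader might infer that benefit is tested on treatment and harm is not, and the documents do not support that. What remains is that MACE has time columns and a censoring rule, and bleeding as such has neither.

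2. **Table 16 shows counts and percentages, not ratios.** This also stands. A reader might infer that any on-treatment excess disappears, but step 4 shows that the absolute difference is largely kept. The relative effect and the printed P value are what weaken.

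3. **Bleeding is neither a primary nor a secondary outcome, and its analysis is labelled descriptive.** This limits how much analysis is warranted. It does not remove the need for a defined period and denominator, and the P column goes beyond description.

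4. **Some bleeding is analysed elsewhere.** Haemorrhagic stroke is part of the stroke outcome (Protocol 5.3.2), which gets Kaplan-Meier rates and hazard ratios, and safety events are listed. But haemorrhagic strokes are pooled there with ischaemic ones, and gastrointestinal bleeding has no such analysis.

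**Conclusion.** The point holds as a gap in period, time split and censoring. On the 0-60 month reading, first-year ratios of 1.5, 2 and 3 appear as about 1.1, 1.2 and 1.4, and the P value weakens with them. The absolute difference keeps about 92% to 98% of its size. These figures rest on a constant aspirin-arm rate and equal rates after month 12. Other time patterns change them (1.11 to 1.33 for R = 2 and 1.22 to 1.67 for R = 3 with k from 0.5 to 2). On the 12-60 month reading, on-treatment bleeding is absent.

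A reader might also infer that subjects unseen after month 12 cause the attenuation. The documents give a rule for losses but no number, and step 5 shows that equal loss does not pull the ratio towards 1. Loss counted as Not occur lowers the raw proportions, and biases the comparison between arms only if it differs by arm. The fault is that the handling is unspecified; no second error is shown.

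The primary analysis is not affected. The change is worth making because it makes the harm estimates interpretable. It will not make them significant, since power is low in either period.

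**What to change.** In SAP 6.2.6 and Table 16:

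- Define the period as starting at randomisation.
- Report each bleeding type separately for months 0-12 and after month 12, by arm: subjects at risk, events, person-years, and cumulative incidence at 12 and 60 months with 95% confidence intervals.
- Censor at last contact, as in SAP 4.3, and state how lost subjects are counted.
- Keep the whole-period count as a secondary line.
- Reconcile the descriptive label in 6.2.6 with the P column: either drop the P values or name the test and its purpose.

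Competing-risk hazard ratios by type, period and contrast would be out of proportion. At an aspirin-arm rate of 0.3% to 1.0% per year and a ratio of 2, the A and T+A arms together would have about 1.5 to 5 first-year events (166 × 0.003 + 168 × 0.006 = 1.5; 166 × 0.01 + 168 × 0.02 = 5.0).

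The cost is some SAP text and a few table rows, with wide intervals because events per period are few. Protocol 3.1 and 5.2 plan to collect event types and times, so the split should need no new data item. The team should confirm that bleeds are dated: Protocol 5.4.1 does not require active collection of all adverse events, and Protocol 7.3 does not list bleeding among the events to be adjudicated.
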